3 ABBREVIATIONS

AE	Adverse event
ADE	Adverse device effect
CI	Confidence interval
CIP	Clinical Investigational Plan
CL	Contact layer
СМС	Carboxymethylcellulose
CRF	Case Report Form
DD	Device deficiency
ET	Early Termination
HAS	Haute Autorité de Santé
ITT	Intent-to-treat
PDMS	Polydimethylsiloxane
PP	Per-protocol
PWS	Periwound skin
VAS	Visual analogue Scale
W.H.A.T.	Wound Healing Analysing Tool

4 STUDY SYNOPSIS

Title	Comparative evaluation of the propertieS of the contact LAyer dressing LOMatuell Pro® versus UrgoTul® in the management of acute wounds					
Project Code/Number	LR/RCTs/01_2017 - 251					
Version and Date	Version 2.0 – March 29, 2019					
Name of Sponsor	Lohmann & Rauscher GmbH Co. KG					
Device Description	Contact layer dressings (Lomatuell Pro® and UrgoTul®). Class IIb medical devices.					
Intended Use	Lomatuell Pro® is intended to be used as a wound dressing for acute wounds according to "Etudes interventionnelles à risques minimes" in French regulation.					
Study design	National, multicenter, prospective, randomized in parallel groups, non-inferiority, open-label investigation study.					
• Study Objectives	 Main study objective To document the non-inferiority of Lomatuell Pro® versus UrgoTul® on pain induced at first dressing removal in the management of acute wounds. Secondary objectives To compare between the two dressings: Complete healing at day 21 Condition of the wound (e.g. wound shift supporting moist wound healing during treatment) Condition of the surrounding skin and efficiency of the CL to drain exudates (exudate management) Global satisfaction of user Subjects' global assessment Safety 					
Inclusion criteria	 Acute wound: traumatic wound (dermabrasion, skin tears, other), small burns 1st and 2nd degree, requiring the use of dressings Acute surgical wound Acute wound size between 3 cm² and 24 cm² (wound could be covered by 2 investigational products maximum) Wound whose duration is ≤ 3 days 					

Version 2.0 – March 29, 2019

	 Both gender with an age ≥ 18 years 						
	 Written confirmation from the study nurse that the patient was informed, orally agreed to participate and to comply with study treatment and planned visits 						
	Subject able to follow the protocol						
	 Infected, moderately to strongly exudative and haemorrhagic wound 						
	 Diagnosed underlying disease (e.g. diabetic neuropathy, stroke, etc.) which as judged by the investigator could interfere with the pain assessment 						
	 Known allergy/hypersensitivity to any of the components of the investigational products 						
Exclusion criteria	 Participation in other clinical investigation within one month prior to start of investigation 						
	 Pregnant or breast-feeding women 						
	 Person protected by a legal regime (tutorship or guardianship) 						
	 Patients unable to manifest an oral consent to participate (e.g. dementia) or to understand the use of the VAS tool Patient not covered by health insurance/social security 						
Study Duration	24 months						
Number of patients	168 patients (i.e. 84 per group)						
•	' ' ' ' ' ' ' ' ' ' ' ' ' ' ' ' ' ' '						
Treatment duration and visits schedule	3 weeks: V1 (D0), V2 (D3±2) and V3 (D21+2 or earlier, as soon as the wound is epithelialized completely)						
Treatment duration	3 weeks: V1 (D0), V2 (D3±2) and V3 (D21+2 or earlier, as soon as						
Treatment duration	3 weeks: V1 (D0), V2 (D3±2) and V3 (D21+2 or earlier, as soon as the wound is epithelialized completely)						
Treatment duration	3 weeks: V1 (D0), V2 (D3±2) and V3 (D21+2 or earlier, as soon as the wound is epithelialized completely) Primary endpoint: Percentage of wound dressing changes associated with a pain <30						
Treatment duration	3 weeks: V1 (D0), V2 (D3±2) and V3 (D21+2 or earlier, as soon as the wound is epithelialized completely) Primary endpoint: Percentage of wound dressing changes associated with a pain <30 mm on VAS at V2 (D3±2).						
Treatment duration	3 weeks: V1 (D0), V2 (D3±2) and V3 (D21+2 or earlier, as soon as the wound is epithelialized completely) Primary endpoint: Percentage of wound dressing changes associated with a pain <30 mm on VAS at V2 (D3±2). Secondary endpoint • Complete healing at V3 (Day D21+2 or earlier, as soon as the wound is epithelialized completely): Percentage of						
Treatment duration	3 weeks: V1 (D0), V2 (D3±2) and V3 (D21+2 or earlier, as soon as the wound is epithelialized completely) Primary endpoint: Percentage of wound dressing changes associated with a pain <30 mm on VAS at V2 (D3±2). Secondary endpoint • Complete healing at V3 (Day D21+2 or earlier, as soon as the wound is epithelialized completely): Percentage of epithelialization of the wound at V3 calculated based on a						
Treatment duration and visits schedule	3 weeks: V1 (D0), V2 (D3±2) and V3 (D21+2 or earlier, as soon as the wound is epithelialized completely) Primary endpoint: Percentage of wound dressing changes associated with a pain <30 mm on VAS at V2 (D3±2). Secondary endpoint • Complete healing at V3 (Day D21+2 or earlier, as soon as the wound is epithelialized completely): Percentage of						
Treatment duration and visits schedule	3 weeks: V1 (D0), V2 (D3±2) and V3 (D21+2 or earlier, as soon as the wound is epithelialized completely) Primary endpoint: Percentage of wound dressing changes associated with a pain <30 mm on VAS at V2 (D3±2). Secondary endpoint • Complete healing at V3 (Day D21+2 or earlier, as soon as the wound is epithelialized completely): Percentage of epithelialization of the wound at V3 calculated based on a blind assessment from photographs using W.H.A.T.						
Treatment duration and visits schedule	3 weeks: V1 (D0), V2 (D3±2) and V3 (D21+2 or earlier, as soon as the wound is epithelialized completely) Primary endpoint: Percentage of wound dressing changes associated with a pain <30 mm on VAS at V2 (D3±2). Secondary endpoint • Complete healing at V3 (Day D21+2 or earlier, as soon as the wound is epithelialized completely): Percentage of epithelialization of the wound at V3 calculated based on a blind assessment from photographs using W.H.A.T. assessment						
Treatment duration and visits schedule	3 weeks: V1 (D0), V2 (D3±2) and V3 (D21+2 or earlier, as soon as the wound is epithelialized completely) Primary endpoint: Percentage of wound dressing changes associated with a pain <30 mm on VAS at V2 (D3±2). Secondary endpoint • Complete healing at V3 (Day D21+2 or earlier, as soon as the wound is epithelialized completely): Percentage of epithelialization of the wound at V3 calculated based on a blind assessment from photographs using W.H.A.T. assessment • Condition of the wound: evaluation by the investigator of 6 condition items at V2 and V3 or Early Termination (ET): bleeding, inflammation, infection, maceration, ratio						
Treatment duration and visits schedule	3 weeks: V1 (D0), V2 (D3±2) and V3 (D21+2 or earlier, as soon as the wound is epithelialized completely) Primary endpoint: Percentage of wound dressing changes associated with a pain <30 mm on VAS at V2 (D3±2). Secondary endpoint • Complete healing at V3 (Day D21+2 or earlier, as soon as the wound is epithelialized completely): Percentage of epithelialization of the wound at V3 calculated based on a blind assessment from photographs using W.H.A.T. assessment • Condition of the wound: evaluation by the investigator of 6 condition items at V2 and V3 or Early Termination (ET):						

	 Condition of the surrounding skin and efficiency of the CL to drain exudates: assessment at V2 and V3 or ET regarding different conditions: inflammatory signs, irritation, allergic rash/eczema, blistering, skin stripping, maceration, dry, trauma to wound edges, product degradation on the skin and hematoma. Global assessment of exudate management (efficiency of the CL to drain exudates to the secondary dressing) Global assessment of the product will be performed by the investigator at V2 and V3 or ET by means of a specific questionnaire Patient's global assessment of the product will be performed by the patient at V3 or ET by means of a specific questionnaire Assessments from study nurse's booklet (at each dressing change) Safety endpoint: frequency and character of device deficiencies (DDs), adverse events (AEs), serious adverse events (SAEs), adverse device effects (ADEs), serious adverse device effects (SADEs)
Double in a bina Combons	
Participating Centers	100 study nurses will participate
Criteria for Early Study Termination	Patients may terminate participation in the study due to following reasons: Consent withdrawal Identification of unacceptable risks, or incidents leading to an unacceptable benefit-risk assessment Premature termination of the investigation decided by the Sponsor Lost to follow-up Occurrence or development of a condition described in the exclusion criteria (i.e. pregnancy, wound infection) throughout the investigation Death
Ethical considerations	This protocol will be submitted to an Ethical Committee

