7.2.2 Investigation Procedures

7.2.2.1 Inclusion visit (V1, D0)

At the inclusion visit (V1, D0) the subject will receive complete information related to the investigation. Prior to any assessment, the oral consent of the patient to participate, according to the "Etudes interventionnelles à risques minimes" French regulations, will have to be obtained by the investigator. Inclusion and exclusion criteria will be checked by the investigator.

The subject will be consecutively allocated to a subject code providing they fulfil all inclusion and none of the exclusion criteria. The subject will be randomized to either receive Lomatuell Pro® or UrgoTul®.

The investigator will report the date of visit, and collect subject information in the case report form (CRF) such as demographic characteristics (gender, age, height, weight), significant medical history including the presence and type of disease which could interfere with the evolution of healing, concomitant therapy, intake of analgesics, characteristics of wound (type and duration of the wound, location, size, assessment of the wound bed (bleeding, maceration, inflammation, infection, ratio necrotic/ fibrinous/ granulation/ epithelisation tissue, and tissue in-growth in the dressing holes) and condition of the surrounding skin (inflammatory signs, irritation, allergic rash/eczema, blistering, skin stripping, maceration, dry, trauma to wound edges, product degradation on the skin, hematoma). Assessment of the amount of exudate (drainage) will be performed after removal of the dressing and before wound cleansing and it will be categorized as none, light, moderate, or heavy.

If applicable, the previous treatment or dressing used will be reported in the CRF. The investigator will also interview the subject about the use of analgesics since the wound occurrence including the frequency of use. These data will be reported in the appropriate form of the CRF.

The wound (with a millimetre ruler) will be photographed by the investigator before the first investigational product application according to the photography guidelines (see Appendix

^{**} will be performed for the patients who discontinued the study preliminary for any reason, instead of the visit V3

^{***}after application of the product at V1, before removal of the product and after application of a new product at V2, before removal of the product at V3 or Early termination visit

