7.7 Evaluation by W.H.A.T

The evaluation by the W.H.A.T. system will be performed by Lohmann & Rauscher with the photographs sent by RCTs on USB Keys.

For determination of the size of the wound area and recording of occurrence of necrotic/fibrinous/ granulation/ epithelisation tissue the validated Wound Healing Analysing Tool (W.H.A.T.) will be used. The wound dressing should be removed from the lesion. The wound should be cleaned with isotonic saline solution and the rest of remedies should be removed. After cleaning the ruler must be placed close to the wound. To achieve a correct picture, the ruler with the square mark had to be placed in the same plane as the lesion. In the case the wound was not plane the ruler has to be applied in the same shape to allow an authenticable digital reproduction of the wound. One digital picture of the lesion will be taken at each visit (in total three pictures of the lesion for each patient for the whole duration of the study); a minimal resolution of 3.0 million pixels is required.

Also, four digital pictures of the investigational product on the wound should be taken during the study (two photographs will be taken after investigational product application before the secondary dressing application on V1 and V2, and two pictures of the wound with the investigational product in place will be taken before the investigational product removal at both visits V2 and V3 (or Early termination visit, if performed instead of V3).

Table 2. Photographs schedule

Version 2.0 – March 29, 2019

	Inclusion visit (V1)	Intermediate visit (V2)	Additional visits	Final visit, or earlier if epithelization (V3)	Early termination visit (whenever possible)
Picture of the wound with the investigational product in place before the investigational product removal (but after removing the secondary dressing)		х		x	x
Picture of the lesion (after cleaning)	x	х		х	x
Picture after investigational product application before the secondary dressing application	х	х			

The pictures should be saved on a USB Key and sent to Lohmann & Rauscher for assessment. Two shipments of the study pictures are planned:

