7.9.1.2 Efficacy analyses

Analysis of the main criterion

The test for the non-inferiority of Lomatuell Pro® vs UrgoTul® for the main criterion will be carried out through a confidence interval (CI) approach. Non-inferiority will be established if the lower unilateral limit of the 97.5% CI in the PP population for the between-treatment difference (Lomatuell Pro® - UrgoTul®) in the percentage of wound dressing associated with a pain < 30 mm on VAS at V2 does not exceed -10%.

Considering that the studied population is "patients with an acute wound" and that the primary endpoint will be assessed at V2 (Day 3±2); we can expect very few drop-outs. We also expect few patients with a major protocol deviation. Therefore, we can conclude that an assumption of 10% attrition rate is acceptable for this study.

In order to unambiguously conclude to non-inferiority in agreement with most of guidelines, the same analysis will be performed on the mITT population. In case of missing data to evaluate the primary criterion, the subjects will be considered as failures. The trial will be considered positive if both approaches support noninferiority.

Adjustment

The frequency of analgesic intake will also be analysed. In case of a significant difference between the 2 dressing groups, the analysis of the primary criterion (painless dressing removals) will be adjusted using a Mantel-Haenszel test.

Analysis of the secondary criteria

The following statistical tests will be used to analyse the secondary criteria according to the criteria type:

- Qualitative nominal criteria will be compared using a Chi² test.
- Qualitative ordinal criteria will be compared using a Mann-Whitney-Wilcoxon test
- Quantitative criteria will be compared using an analysis of variance (ANOVA)

Degree of significance

The criteria for which the degree of significance of the bilateral test will not exceed 0.05 (statistically significant difference) will highlight the specificities between the 2 groups of dressing.

Percentage of complete healing at V3

A wound will be considered as completely healed when there is 100% of epithelialization (first epithelia layer) of the wound. The percentage of wounds healed will be calculated based on a blind assessment from photographs using W.H.A.T.

Assessment of the wound condition

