The wound bed condition will be evaluated at V1, V2 and V3 or ET regarding 6 condition items - bleeding, maceration, inflammation, infection, ratio necrotic/ fibrinous/ granulation/ epithelisation tissue, and tissue in-growth in the dressing holes by means of the following 4-points scale: *none*, *mild*, *moderate*, *severe*. The percentage of each modality for each condition items will be calculated.

Assessment of the surrounding skin condition

The condition of the surrounding skin will be assessed at V1, V2 and V3 or ET regarding different conditions: inflammatory signs, irritation, allergic rash/eczema, blistering, skin stripping, maceration, dry, trauma to wound edges, product degradation on the skin, hematoma, other. These condition items will be assessed by means of the scale *Yes/No*. The percentage of each modality will be calculated.

Wound closure according to inclusion wound exudation status.

This will use a Cochran-Mantel-Haenszel test including treatment groups and baseline wound exudation status (none, light and moderate/heavy).

Global assessment of the dressing by the investigator

The global assessment of the dressing will be performed by the investigator at V2 and V3 or ET. Each item will be evaluated by means of the following scale: *very good, good, poor, and very poor*.

The percentage of each modality of each criterion (ease of handling, ability to maintain its integrity, ease of application, ability to be repositioned during application, conformability, wound adhesion, ability of dressings to stay in place, transparency, ability to transfer wound fluid to the secondary dressing, ease / speed of removal, overall impression, and absence of residue) will be calculated.

Global assessment of the dressing by the subject

A global assessment of the dressing will be performed by the subject at V3 or ET. Each item (ability to maintain its integrity, ability of dressings to stay in place, transparency, comfort of the patient, ability to transfer wound fluid to the secondary dressing, ease/speed of removal, overall impression) will be evaluated by means of the following scale: *very good, good, moderate, poor, very poor.* The percentage of each modality will be presented.

Assessments from the study nurse's booklet at each dressing change

The total number of dressing changes will be calculated and the mean value of dressing changes will be calculated.

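### Free improvement on a secondary endpoint: adjust the complete-healing comparison for V1 wound area, which spans 3-24 cm² at entry and is already measured

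*Protocol*

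**What the plan says.** Entry: Protocol section 4 (repeated in 7.3.1) sets "Acute wound size between 3 cm² and 24 cm² (wound could be covered by 2 investigational products maximum" and "Wound whose duration is ≤ 3 days".

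Recording: at V1 the nurse enters "characteristics of wound (type and duration of the wound, location, size, assessment of the wound bed" (section 7.2.2.1). The wound is photographed with a ruler before the first product goes on. Section 7.7 applies W.H.A.T. to the lesion picture from each visit: "For determination of the size of the wound area and recording of occurrence of necrotic/fibrinous/ granulation/ epithelisation tissue".

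Analysis (section 7.9.1.2): healing means full epithelialization, and "The percentage of wounds healed will be calculated based on a blind assessment from photographs using W.H.A.T". The general rule for secondary criteria is "Qualitative nominal criteria will be compared using a Chi² test". A separate paragraph on wound closure by exudation at inclusion adds: "This will use a Cochran-Mantel-Haenszel test including treatment groups and baseline wound exudation status (none, light and moderate/heavy". No healing analysis uses wound area.

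Allocation: section 7.9.3 describes permuted blocks and mentions no stratification by wound size.

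SAP: the one supplied states in its section 4 that it was written for a different product's protocol. It contains no healing comparison for this trial.

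**The concern.** Complete healing is a yes/no result against a fixed limit of 21(+2) days, and it is the first secondary objective listed. A wound of 24 cm² has eight times the area and 2.8 times the radius of one of 3 cm², so it is plausible that starting area affects the chance of closing in time. If it does, two things follow. An unadjusted comparison is less precise than one that uses area. And in a trial where one arm happens to receive larger wounds, the crude healing difference is shifted, with no prespecified adjusted result to set beside it. An adjustment chosen after the data are seen would carry less weight, particularly in an open-label trial.

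**Working it through.** **1. The plan's own figure.** The protocol gives a sample size only for the primary endpoint. With 95% in both arms, a 10% margin, one-sided 2.5% and 80% power: n = (1.960 + 0.842)² × 2 × 0.95 × 0.05 / 0.10² = 74.6, so 75 per arm. Then 75/0.9 = 83.3, so 84. Both figures match section 7.9.2. No power, expected rate or margin is stated for healing. As a guide, a Chi² at 84 per arm has 58.7% power for 80% v 65% healed and 32.0% for 80% v 70%.

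**2. Spread of area.** 24/3 = 8, or three doublings; the radius ratio is √8 = 2.83.

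**3. How often the arms differ in size.** For the share of wounds above the median, SE = √(2 × 0.25/84) = 0.077. A difference of 10 points or more then has probability P(|Z| ≥ 0.10/0.077) = 0.195, about one trial in five. On the log scale, assuming area log-uniform on 3-24 cm², the SD of log2 area is 3/√12 = 0.866. The arm difference has SD 0.866 × √(2/84) = 0.134. A 1-in-20 imbalance is 1.96 × 0.134 = 0.262 doublings, about a 20% difference in geometric mean area.

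**4. What an imbalance does to the estimate.** Shift = imbalance × closure gap between above- and below-median wounds. The gap is not in the documents. If closing time is proportional to √area with lognormal scatter (SD of log 0.25-0.40) and 80-90% of control wounds close, the gap is about 14-37 points. A 10-point imbalance then shifts the difference by 0.10 × 14 = 1.4 to 0.10 × 37 = 3.7 points. For comparison, the SE of the healing difference is √(2 × 0.8 × 0.2/84) = 6.2 points at 80% healed and √(2 × 0.9 × 0.1/84) = 4.6 points at 90%.

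**5. Power, by assumed strength of area.** Simulation with 84 per arm, log-uniform area, a true 15-point healing difference and 6,000 trials per scenario. Chi² is set against a logistic model with log2 area:

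| Odds ratio per doubling | Control healed | Chi² | Adjusted |
|---|---|---|---|
| 0.9 | 60% | 50.1% | 49.5% |
| 0.9 | 80% | 59.4% | 59.8% |
| 0.7 | 70% | 51.4% | 52.6% |
| 0.7 | 80% | 58.2% | 59.0% |
| 0.5 | 70% | 51.9% | 55.1% |
| 0.5 | 80% | 60.1% | 62.7% |
| 0.35 | 70% | 52.5% | 60.0% |
| 0.35 | 80% | 59.4% | 66.0% |

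The √area model of step 4 corresponds to odds ratios of about 0.06-0.21, a much stronger effect of area. If one dressing lengthens closing time by 20%, power there is 32-75% for Chi², 35-84% for a Cochran-Mantel-Haenszel (CMH) test by area tertile (gain 3-17 points) and 38-86% for logistic regression on log area (gain 5-20). Widening the scatter to SD 0.6-0.8 (odds ratio about 0.31-0.47) cuts the gain to about 0-3 points. That is below the table's gain at 0.35 because a 20% delay then produces a smaller healing difference than 15 points.

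**6. Type I error.** Overall, the Chi² rejects a true null in 4.6-5.5% of trials in every scenario of the table's model, and in 4-6% under the √area model. Among only the null trials with a 1-in-20 or worse area imbalance, it rejects in about 4-5% (odds ratio 0.9), 4-8% (0.7), 6-10% (0.5) and 10-13% (0.35). The adjusted test rejects in about 3-8%. Each conditional rate rests on about 300 trials, with a Monte Carlo SE of 1-2 points.

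**The case against.** An unadjusted test in a randomised trial is valid, and its 5% error rate already averages over chance imbalances. The shift in step 4 is smaller than one standard error of the healing difference. Healing has no stated power or success rule, and the trial is judged on V2 pain. The documents do not rank area above wound type, depth or location. Entry mixes abrasions, skin tears, burns and surgical wounds, which may add enough scatter to make area a modest predictor. The plan already prespecifies one covariate for closure. All of this stands, and it limits the point to an efficiency gain.

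It does not remove the point. The exudation analysis cannot stand in for area. Section 7.3.2 lists moderately to strongly exudative wounds among the exclusions, so that analysis has in effect two strata, neither defined by size.

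A reader might infer four stronger things, none of which the documents support:

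- That a size imbalance makes the Chi² misleading in general. Overall type I error is not inflated; the problem is conditional on an observed imbalance and is marked only if area is very strongly prognostic.
- That the power loss is large. Gains well above 8 points need odds ratios of 0.06-0.21 per doubling, for which the documents give no evidence.
- That this is the only comparison able to show slower healing. The CMH test of closure by exudation is another, and the epithelisation tissue ratio is also assessed at V1, V2 and V3.
- That wound age needs adjustment too. It spans only 0-3 days, and no calculation supports including it.

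The Chi² is itself an inference. The synopsis words the endpoint as a percentage of epithelialization, which as a continuous measure would fall under ANOVA. Section 7.9.1.2, which reports the percentage of wounds healed, supports the binary reading.

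**Conclusion.** The point holds as a free improvement to a secondary analysis, not as an error. The planned healing comparison, read as a Chi², is valid but ignores a recorded baseline measure with an eight-fold range. Under the stated assumptions, adjustment gains about 0-1 power point if area is weakly to moderately prognostic (odds ratio 0.7-0.9 per doubling), 0-4 near 0.5, 5-8 at 0.35, and up to about 20 only in the extreme case (0.06-0.21). When the arms differ by 10 points in above-median wounds, the crude estimate moves by about 1-4 points, given a closure gap of 14-37 points. All these figures use the full 84 per arm, so they make no allowance for the 10% attrition. How prognostic area is, and the healing rate, are assumptions. The primary non-inferiority conclusion on pain is unaffected.

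**What to change.** In section 7.9.1.2, prespecify that complete healing is compared with adjustment for V1 wound area, in one of two forms:

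- a Mantel-Haenszel risk difference with 95% CI, stratified by tertile of V1 area, with cut-points fixed on data pooled over arms; or
- a logistic model with log V1 area, reported as a standardised risk difference with 95% CI.

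Take area from the blinded W.H.A.T. reading of the V1 photograph, or from the nurse's V1 size if the photograph cannot be read. Keep the Chi² as the unadjusted companion and the exudation CMH as planned. Wound duration need not be a required covariate. State in the same place that the endpoint is binary, so that the choice of test no longer has to be inferred.

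Cost: a sentence or two in the analysis section, with no new data. If nearly all wounds close, or area proves unimportant, the adjusted and unadjusted results should largely agree.
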